- r. Tumor assessments will be performed based on irRECIST and modified RECIST1.1. Treatment decisions will be based on irRECIST. Tumor assessments will be carried out during the Pretreatment Phase and then every 6 weeks (during the 6th week; counting from C1D1) during treatment cycles in both the Treatment Phase and the Extension Phase. CT scans (with oral and intravenous contrast) of chest, abdomen, and pelvis and of other known sites of disease will be obtained at Screening (within 28 days prior to Cycle 1/ Day 1), using the above tumor assessment schedule, and as indicated clinically. Skin lesions may only be considered as non-index lesions (no photographs required) or as new lesions to add to the tumor burden sum. Subjects with SCCHN must also have head and neck scans performed at all tumor assessment timepoints.
- MRI scans may be used instead of CT scans for (head, neck) abdomen and pelvis; however, chest must be assessed using CT. Chest disease may not be followed using chest x-ray. CT scans should be performed with oral and iodinated IV contrast and MRI scans with IV gadolinium chelate unless there is a medical contraindication to contrast. If iodinated IV contrast is contraindicated, chest CT should be performed without IV contrast. The same method of assessment must be used at all time points as used at Screening.
- s. Screening brain scans will be performed by MRI pre- and post- gadolinium or CT with contrast within 4 weeks prior to C1D1. During the Treatment Phase, CT/MRI of the brain will be performed if clinically indicated, and within a target of 1 week after a subject achieves a irCR. For subjects with history of treated brain metastases, brain scans will be performed at every tumor assessment time point. The same methodology and scan acquisition techniques used at screening should be used throughout the study to ensure comparability.

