##### **Secondary Efficacy endpoints:**

- Objective response rate

The ORR is the proportion of subjects achieving a best overall response of confirmed partial or complete response (irPR + irCR), according to irRECIST ([Appendix 1](#)) from first dose date until disease progression/recurrence. Subjects who do not have a tumor response assessment for any reason will be considered nonresponders and will be included in the denominator when calculating the response rate.

- Duration of response

Duration of response is defined as the time from the date of first documented confirmed irCR/irPR until the first documentation of confirmed disease progression or death, whichever comes first.

- Progression-free survival

Progressive-free survival is defined as the time from first dose date to the date of the first documentation of confirmed disease progression or death (whichever occurs first) using irRECIST. The censoring rule for events will be defined in the SAP.

- Disease control rate

The DCR is the proportion of subjects achieving irPR + irCR + irSD from first dose date until disease progression/recurrence.

- Clinical benefit rate

The CBR is the proportion of subjects achieving irPR + irCR + irSD [lasting at least 24 weeks] from first dose date until disease progression/recurrence.

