5.4.1 Efficacy Analyses According to immune-related RECIST (irRECIST)

Tumor assessments and overall response to the treatment according to irRECIST are presented in Section 13.2. The confirmation of progressive disease (irPD) is required at least 4 weeks after the initial irPD. If irPD at two consecutive tumor assessment visits with less than 4 weeks, the additional confirmation of irPD visit is required. If irPD is confirmed, the documented start date of irPD is determined as follows:

1. The date of the initial irPD if it is confirmed on consecutive tumor assessment visits.
2. The date of the second irPD if the initial irPD is confirmed not on consecutive tumor assessment visits.

The best overall response (BOR) is defined as follows:

- **irCR**

To achieve BOR of irCR, irCR must be observed at two consecutive tumor assessment visits with at least 4 weeks apart before the confirmed irPD, death, or end of study (whichever occurs first). If complete response at two consecutive tumor assessment visits with less than 4 weeks, the confirmation of irCR at the next assessment visit is required. The documented start date of irCR is defined as the date of the initial irCR.

- **irPR**

When BOR of irCR is not achieved, BOR of irPR can be achieved by that an initial irPR is confirmed by irPR or irCR at next consecutive visit (≥ 4 weeks after the first irPR response). If irPR or irCR happens at two consecutive tumor assessment visits within 4 weeks, the additional confirmation of irPR (irPR or irCR in a later visit) is needed for BOR of irPR. The documented start date of irPR is the date of the initial irPR.

- **irSD**

If the documented start date of irPD is not the first evaluable tumor assessment visit after the first dose of study drug and the BOR is not a confirmed irCR/irPR, then the BOR is stable disease (irSD) when the duration of irSD is no less than 5 weeks. The duration of irSD is defined as the time from the first dose date to the documented start date of irPD, death, or the last evaluable tumor assessment (whichever occurs first).

- **irPD**

If the documented start date of irPD is the first evaluable tumor assessment visit after the first dose of study drug, then the BOR is irPD.

Table 1 listed general rules in the derivation of BOR with two consecutive tumor response results.

Table 1 Derivation of BOR with Two Consecutive Tumor Response Results

| Timepoint 1 Initial Response | Timepoint 2 Follow-up Response ≥ 4 weeks | BOR |

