The disease control rate (DCR) is the proportion of patients achieving the BOR of confirmed irCR, confirmed irPR or irSD with the duration of at least 5 weeks. The count and percentage for the DCR will be summarized by dose group.

Clinical Benefit Rate (CBR)

The Clinical benefit rate (CBR) is the proportion of patients achieving the BOR of confirmed irCR, confirmed irPR or durable irSD (i.e., the duration of at least 24 weeks). The count and percentage for the CBR will be summarized by dose group.

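### Durable irSD needs 24 weeks from first dose, but the on-schedule Week 24 scan falls short of that, so stability shown there is lost from CBR when it is the last evaluable scan

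*SAP*

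**What the plan says.** Three rules meet here.

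- **Threshold.** Protocol 9.7.1.1 includes in CBR "irSD [lasting at least 24 weeks". SAP 5.4.1 repeats this as "durable irSD (i.e., the duration of at least 24 weeks".
- **Clock.** SAP 5.4.1 starts irSD duration at the first dose date and stops it at the "documented start date of irPD, death, or the last evaluable tumor assessment (whichever occurs first". Confirmed irPD takes "The date of the initial irPD if it is confirmed on consecutive tumor assessment visits", so its date is normally the first scan that shows it.
- **Scan schedule.** Protocol Table 6, footnote r, sets tumor assessments "every 6 weeks (during the 6th week; counting from C1D1". Protocol 9.5.2 and SAP 13.1 say the same. The bone-scan footnote (t) follows the same logic for its 24-week scan.

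For the disease control rate (DCR), SAP 5.4.1 uses a shorter minimum: "then the BOR is stable disease (irSD) when the duration of irSD is no less than 5 weeks". The SAP gives no tolerance around 24 weeks and no rule on whether a duration is a date difference or a date difference plus one day.

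**The concern.** The 24-week threshold is a calendar duration, but stability is observed only at scans, and the scheduled scan that should establish 24 weeks takes place before 24 weeks have elapsed. A subject followed on schedule and stable at the Week 24 assessment can therefore miss the threshold by one to seven days. The clock also ends at the irPD date and not at the last scan showing stability, so a subject whose stability was last documented at Week 18 can pass.

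In some follow-up patterns, CBR would thus exclude a subject shown stable at Week 24 and include one never shown stable after Week 18. CBR is a named secondary endpoint reported by dose group, and in cohorts of 6 a single subject is visible in the result.

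**Working it through.** **Inputs.** Threshold of 24 weeks = 168 days (SAP 5.4.1; Protocol 9.7.1.1). Clock from first dose, C1D1 = Day 1 (SAP 5.4.1). Scans in the last week of each six-week block (Table 6, footnote r). Cycles of 21 days.

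**Formulas.** The window for the Week *w* scan is Day 7(*w*-1)+1 to Day 7*w*. Elapsed days = scan day minus 1. Under a +1-day convention, duration equals the scan day.

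**Check on the SAP's own 5-week minimum.** The Week 6 scan falls on Days 36-42 = 35-41 elapsed days = 5.00-5.86 weeks. All 7 window days meet 35 days, and Day 36 meets it exactly. The DCR minimum therefore sits at the lower edge of its scan window.

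**The same check at 24 weeks.** Day 7×23+1 = 162 to Day 7×24 = 168. Elapsed: 161-167 days = 23.00-23.86 weeks.

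- Date difference: 0 of 7 window days reach 168.
- +1-day convention: 162-168 days = 23.14-24.00 weeks, so 1 of 7 (Day 168).

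**Scenarios** (date difference; the last column uses the definition proposed under the fix)

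| Course | Elapsed days | Weeks | In CBR now | In CBR if redefined |
|---|---|---|---|---|
| irSD Day 165, last evaluable scan | 164 | 23.43 | No | Yes |
| irSD Day 168, last evaluable scan | 167 | 23.86 | No (yes under +1) | Yes |
| irSD Day 165, death Day 190 | 164 | 23.43 | No | Yes |
| irSD Day 165, irSD Day 207 | 206 | 29.43 | Yes | Yes |
| irSD Day 165, irPD Day 207, confirmed Day 249 | 206 | 29.43 | Yes | Yes |
| irSD Week 18, irPD Day 168, confirmed later | 167 | 23.86 | No (yes under +1) | No |
| irSD Week 18, irPD Day 169, confirmed later | 168 | 24.00 | Yes | No |
| irSD Week 18, irPD Day 170, confirmed later | 169 | 24.14 | Yes | No |
| irSD Week 18, Week 24 missed, irPD Day 207, confirmed Day 249 | 206 | 29.43 | Yes | No |

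The last row arises because SAP 5.4.1 ignores a single missing assessment between two evaluable ones.

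**How Week 24 becomes the last evaluable scan.** Under Protocol 9.7.1, cutoff comes when the last subject completes 6 cycles: 6×21 = 126 days. A subject who started *k* days earlier is then at Day 126+*k*. Week 24 can be that subject's latest scan when 126+*k* lies between Day 162 and Day 209, so *k* is about 36-83 days (roughly 5-12 weeks), depending on where in the windows the scans fell. SAP 3.2 allows an earlier cutoff. Death, withdrawal, new anticancer therapy or a non-evaluable Week 30 scan have the same effect.

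**Size per subject.** 1/6 = 16.7 points; 1/16 = 6.25, or 6.3 points. These grow if the Response Evaluable Set (SAP 5.4) is smaller than the cohort.

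**The case against.** Much of the case on the other side stands, and it limits the point.

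- A reader might infer that stability at Week 24 generally fails CBR. It does not. Scanning continues every six weeks, and any evaluable Week 30 scan, even one showing irPD, gives about 29 weeks. The loss occurs only when Week 24 is the last evaluable assessment.
- A reader might take the problem as independent of data cutoff. It is not; cutoff is one of the main routes to it.
- A reader might think the opposite error is easy to produce, because C9D1 is Day 8×21+1 = 169 and Table 6, footnote c, allows ±3 days. That window is given to the Day 1 and Day 8 cycle visits. Scans are timed separately from C1D1, so irPD first seen on Day 169 or 170 needs a late or unscheduled scan. Otherwise the Week 24 scan must be missed.
- A reader might infer that a misclassified CBR feeds selection of the recommended Phase 2 dose (RP2D). Protocol 9.1.1.4 refers to clinical benefit and to available evidence of activity, without naming CBR. It places the selection after the last escalation subject finishes Cycle 1.
- The 0-of-7 result assumes a date difference. SAP section 9 leaves programming rules to separate documents, which may state a +1-day convention; Day 168 then passes. That rescues one day of seven. It also lets irPD first seen on Day 168, within the window, count as durable.
- Running the clock to the irPD date is also the SAP's PFS convention. That is a legitimate choice for a time-to-event endpoint. For a yes/no claim of 24-week stability, it credits time during which stability was not observed.
- CBR has no test, success threshold or sample-size role, so no error rate is affected.

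**Conclusion.** The mismatch is real and follows from the documents' own text. An on-schedule Week 24 scan gives 23.0-23.9 weeks against a 24-week threshold, while the 5-week minimum in the same section fits its own scan window. The consequence is conditional. Subjects stable at Week 24 are lost only when that scan is their last evaluable one, and subjects last shown stable at Week 18 are gained only through a late, unscheduled or missed Week 24 scan.

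The number affected is unknown, since the documents give no accrual, discontinuation or progression rates. Each affected subject moves CBR by 16.7 points in a cohort of 6 or 6.3 points in 16. This rests on C1D1 being both Day 1 and the first dose date, and on durations taken as date differences; under +1 counting the shortfall covers 6 of 7 window days. The effect is confined to a descriptive secondary endpoint and its modified RECIST 1.1 counterpart.

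**What to change.** In SAP 5.4.1, define durable irSD by the assessment and not by elapsed time:

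- an evaluable scan in or after the Week 24 window (on or after Day 162) with a time-point response of irSD or better; and
- no confirmed irPD, dated by the existing rules in 5.4.1, on or before that scan.

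An unconfirmed irPD at Week 24 followed by a later scan showing irSD or better still qualifies, in keeping with the confirmation rule. State the day-count convention for all durations. Apply the same definition under SAP 5.4.2 for modified RECIST 1.1, using PD without confirmation.

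Lowering the threshold to 23 weeks (161 days) is not enough. It would admit all 7 window days, but it would also count a subject whose on-time Week 24 scan shows irPD (161-167 days).

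The cost is a short change to the SAP and no new data. The downside is that the criterion becomes stability through the Week 24 assessment, with a minimum of 23 weeks. Because Protocol 9.7.1.1 says 24 weeks, the change should be recorded in SAP section 7, which currently reports no changes to the planned analysis.

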5.4.2 Efficacy Analyses According to Modified RECIST 1.1 (mRECIST 1.1)

Modified RECIST 1.1 is the same as the RECIST 1.1 but allow to choose up to ten (10) target lesions and five (5) per organ at baseline instead of 5 target lesion (and 2 per organ) if clinically relevant via CT/MRI scans. In contrast to irRECIST, Modified RECIST 1.1 does not require the confirmation of progressive disease (PD).

The best overall response (BOR) based on mRECIST 1.1 is defined similarly as that according to the irRECIST (Section 5.4.1) except that the confirmation of PD is not required.

Objective response rate, time to response (TTR), duration of response (DOR), progression-free survival (PFS), disease control rate (DCR), and clinical benefit rate (CBR) according to modified RECIST 1.1 will be analyzed similarly to those according to irRECIST (Section 5.4.1).

5.4.3 Overall Survival (OS) Analyses

Overall survival rate will be presented at each evaluation visit by dose group. The survival (function) curve and median survival time will be estimated and reported by the Kaplan-Meier method.

5.4.4 FDG-PET Analyses

The change from baseline at Week 6 and Week 12 will be summarized by the descriptive statistics for the following FDG-PET/CT measurements:

- Sum of maximum for target lesions (Single pixel, unitless)
- Maximum SUV (single pixel, unitless)
- Maximum SUV (1 cm spot, unitless)
- Average metabolic SUV (unitless)
- Metabolic Volume (mm²)
- Total Tumor Volume (mm²)

The shift table from baseline for overall status of none-target lesions (present/absent) and status of new lesions (present/absent) will be tabulated at Week 6 and Week 12.

FDG-PET/CT as a biomarker of response analyses will be detailed in a separate biomarker analysis plan.

5.5 Pharmacokinetic, Pharmacodynamic, and Pharmacogenomic/Pharmacogenetic Analyses

Plasma concentrations were obtained from blood samples drawn at each study visit during the treatment period (C1D1 and C1D8). Details of the analysis methods for population PK/PD modeling will not be described in this SAP but will be described in a separate analysis plan.

5.5.1 Pharmacokinetic Analyses

Blood samples for PK analyses will be collected during Cycle 1 on Day 1 and Day 8 at predose (0 h), 0.5, 1, 2, 4, 6, 8, and 10 and 24h postdose. Urine samples for PK analyses will be collected during the Dose Escalation part only Cycle 1.

Concentration data for E7046 and its major metabolite M1 will be analyzed and summarized by time point and dose group, respectively. Linear/semi-log plots of individual concentration data and mean concentration with SD over time will be presented for E7046 and its major metabolite M1 by dose group based on the pharmacokinetic analysis set.

For Cycle 1 on Day 1 and Day 8, PK parameters will be derived using non-compartmental methods for E7046 and its metabolite include, but are not limited to:

- maximum concentration (Cmax),
- time to maximum concentration (tmax),
- area under the curve from 0 to 24 hours (AUC0-24),
- area under the curve from 0 to infinity (AUC0-inf) ,
- elimination half life (t1/2); and if data permit,
- total body clearance (CL),
- volume of distribution (Vd),
- renal clearance (CLr),
- accumulation ratio (Rac),
- fraction excreted (fe),
- cumulative amount excreted in urine (Ae).

Descriptive statistics will be used to summarize PK parameters for E7046 and its metabolite by dose group based on the pharmacokinetic analysis set.

When presenting individual/raw values and summary statistics, the following rule will be applied: for drug concentrations and concentration-dependent pharmacokinetic parameters, all summary statistics (mean, median, geometric mean, standard deviation [SD], and coefficient variation [CV]) will have 3 significant digits. For t1/2, raw values and median have fixed 2 decimal places.

In addition, plots of AUC, Cmax and CL versus dose as well as cumulative Ae versus time intervals (0-6 hours, 6-12 hours and 12-24 hours) will be presented for E7046 and its major metabolite M1 based on the pharmacokinetic analysis set.

5.5.2 Pharmacodynamic and Pharmacogenomic Analyses

Pharmacodynamics (PD) biomarkers including Proof of Mechanism (POM) biomarkers to show target engagement and Proof of Principle (POP) biomarkers to show impact of E7046 treatment on disease will be evaluated from collected samples.

Proof of Mechanism may be demonstrated by an alteration in expression of EP₄ response genes and/or proteins, as EP₄ is the molecular target of E7046.

POP for E7046 could be a change in intratumoral immune cell populations consistent with inhibition of EP₄ signaling such as a decrease in the ratio of M2/Total TAM or an increase in the number of CD8+ T cells. POP could also be a decrease in the number or ratio of MDSC in circulation.

Results from biomarker studies will be used to aid the selection of dose and for correlation with drug efficacy. The biomarker assessments planned for this study are summarized in Table 2.

Table 2 Biomarker assessments

| Biomarker sample | Time points | Analyses | Potential Utility |
|---------------------|--|---|-------------------|
| Serum protein | C1D1 predose, 24hr after first dose, C1D8, C1D15 | TAM/MDSC-related cytokines, eg, PGE ₂ , Renin) | POM |
| Serum mRNA | C1D1 predose, 24hr after first dose, C1D8, C1D15 | Gene expression, eg, REN, EP ₄ | POM |
| Paired tumor biopsy | Predose and during Cycle 2 | T cell and macrophage infiltration | POP |
| Archived tumor | Screening | To be decided | |
| Whole blood | Baseline, Predose on C1D1, C1D8, C1D15, C2D1, C3D1, and C5D1 | Circulating MDSC | POP, POM, PS |
| Blood plasma | Baseline, time points for at each CT tumor assessment, and End of Treatment | Cell-free nucleic acid | |
| Whole blood DNA | Screening | Pharmacogenomic analysis | PG |
| Urine | Cycle 1 Day 1 pre-dose (0-hr) and Cycle 1 Day 1 and Day 8 post-dose to 6hr, 6 to-12hr, 12 to 24hr. | PGE ₂ metabolite | POM |

C1D1 = Cycle 1 Day 1, MDSC = myeloid-derived suppressor cell, PG = prostaglandin, PGE = prostaglandin e2, POM = Proof of Mechanism, POP = Proof of Principle, PS = patient stratification, REN = renin, TAM = tumor-associated macrophages.

Pharmacodynamic (PD), pharmacogenomic (PG) or other biomarker analyses will be detailed in a separate biomarker analysis plan.

5.6 SAFETY ANALYSES

All safety analyses will be performed on the Safety Analysis Set. Safety data will be presented by dose group (although there will be no formal statistical comparison in the safety analysis) and

will be summarized on an “as treated” basis using descriptive statistics (e.g., n, mean, SD, median, Q1, Q3, minimum, maximum for continuous variables; n (%)) for categorical variables). Study Day 1 for all safety analyses is defined as the date of the first dose of study drug. Safety variables include treatment-emergent adverse events (TEAEs), 12-lead ECG results, clinical laboratory tests and vital signs. The incidence of TEAEs, clinical laboratory parameters and vital signs as well as their changes from baseline will be summarized using descriptive statistics. Abnormal values will be flagged.

5.6.1 Extent of Exposure

Number of cycles completed, duration of treatment and cumulative total dose will be summarized by dose group.

5.6.2 Dose Limiting Toxicity

After all subjects in a dose level tested complete the first treatment cycle, safety information for those subjects will be reviewed by the Eisai clinical team together with the principal investigator/s and dose limiting toxicity (Yes/No) and reason(s) (see Section 13.3) for experiencing a dose limiting toxicity (DLT) as well as date and dosage of study drug when the DLT occurred will be determined for each subject. This result will be listed for the study report.

5.6.3 Adverse Events

The adverse event verbatim descriptions (investigator terms from the eCRF) will be classified into standardized medical terminology using the Medical Dictionary for Regulatory Activities (MedDRA) version 18.0 or later. Adverse events will be coded to primary System Organ Class (SOC) and preferred term (PT) using MedDRA.

A treatment-emergent AE (TEAE) is defined as an AE that emerged during treatment (from first dose to 30 days after last dose of study drug) and

- had been absent at pretreatment (Baseline) or
- reemerged during treatment, having been present at pretreatment (Baseline) but stopped before treatment, or
- worsened in severity during treatment relative to the pretreatment state, when the AE was continuous.

Only those AEs that are treatment emergent will be included in summary tables. All AEs, treatment emergent or otherwise, will be presented in subject data listings.

The incidence of TEAEs will be reported as the number (percentage) of subjects with TEAEs within SOC and PT. Subjects will be counted only once within a SOC and PT, even if the subject experienced more than one TEAE within a specific SOC and PT, and the subject will be counted with the worst grade for that particular AE. The number (percentage) of subjects with TEAEs will also be summarized by highest Common Terminology Criteria for Adverse Events (CTCAE) grade. The number (percentage) of subjects with treatment-related TEAEs will also be summarized by SOC and PT. Treatment-related TEAEs include those events considered by the investigator to be possibly or probably related to study treatment. In summary, the following TEAE tables will be provided:

- Overview of TEAEs
- TEAEs by SOC and PT
- TEAEs by SOC, PT, and CTCAE grade
- TEAEs with CTCAE grade 3 or 4 by SOC and PT
- TEAEs that led to drug discontinuation by SOC and PT
- TEAEs that led to dose reduction by SOC and PT
- TEAEs that led to dose interruption by SOC and PT
- Treatment-related TEAEs by SOC and PT
- Treatment-related TEAEs with CTCAE grade 3 or 4 by SOC and PT
- Treatment-emergent serious AEs by SOC and PT
- Treatment-related treatment-emergent serious AEs by SOC and PT

Subjects AE listings (treatment emergent or not) will be provided. In addition, the following subject AE listings will be provided:

- All fatal adverse events.
- All non-fatal serious adverse events (SAEs)
- All non-fatal non-serious treatment-emergent adverse events that led to discontinuation of treatment

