### 9.1.1 Dose Escalation

#### 9.1.1.1 Dose Escalation Design

E7046 will be tested in sequential escalating dose cohorts of 6 subjects per cohort, at the dose levels shown in [Table 1](#). Subjects will be assigned to a dose level in the order of study entry. Intermediate dose levels may be explored.

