**Table 1 Dose Cohorts in E7046 Dose-Escalation**

Dose level	No. of Subjects	E7046 Dose
-1	6	75 mg QD
1	6	125 mg QD
2	6	250 mg QD
3	6	500 mg QD
4	6	750 mg QD

QD = once daily.

The schema for dose escalation is adopted and modified from the traditional 3+3 design and is shown in [Figure 3](#). Dose limiting toxicities are defined in [Section 9.1.1.2](#).

Enrollment for first dose cohort (125 mg QD): (see Figure 3 Panel B)

In the first cohort, staggered dosing will be employed as described below.

Suspected severe immune reactions (ssIR) are defined as listed in the CTCAE v4.03 "Immune System Disorders", including Allergic Reaction, Anaphylaxis, and Cytokine Release Syndrome.

*First 3 subjects (Subjects 1, 2, and 3)*

- Initially one subject (Subject #1) will be enrolled and dosed.
  - If after 14 days of dosing no suspected severe immune reactions are observed, another 2 subjects (Subjects # 2 and 3) will be enrolled and dosed.
  - If within the first 14 days, Subject #1 experiences a suspected severe immune reaction, another subject (Subject #2) will be enrolled and dosed.
    - If after 14 days of dosing no suspected severe immune reactions are observed for Subject #2, another subject (Subject #3) will be enrolled and dosed.
    - If within the first 14 days, Subject #2 also experiences a suspected severe immune reaction, enrollment in this dose cohort will stop. A lower dose level of 75 mg QD (Dose Level -1) may be tested. Enrollment of the 6 subjects at Dose Level -1 will follow the same staggered schema as described for Dose Level 1.

*Next 3 subjects (Subjects 4, 5, and 6)*

- After evaluation of the first 3 subjects for DLTs after 21 days (Cycle 1), enrollment will continue as follows:
  - If  $\leq 1$  of 3 first subjects experiences DLTs in Cycle 1, the remaining 3 subjects (Subjects # 4, 5, and 6) in the first cohort will be enrolled and treated.
  - If  $>1$  of 3 first subjects experiences DLTs in Cycle 1, a lower dose level of 75 mg (dose level -1) will be tested, following the same enrollment schema as described for Dose Level 1.

Enrollment of subsequent dose cohorts:

[figure not shown]
- There will be no staggered dosing after the first dose cohort, however the subject enrolment will be controlled so that no more than one subject will be dosed on the same day.
- If  $\geq 2$  of 6 subjects in any dose cohort experiences a DLT, then dose escalation will be stopped.

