#### 9.1.1.4 Selection of the Recommended Phase 2 Dose

The RP2D will be selected based on integrated evaluation of safety, tolerability, clinical benefit, PK, and PD data, for all dose levels tested. The investigator and sponsor will jointly evaluate the data and select the RP2D.

Selection of the RP2D will take place after the last subject in the Dose Escalation part completes the Treatment Phase ([Section 9.1.3.2](#)).

The RP2D will be selected according to the following guidelines:

1. The RP2D will not exceed the MTD.
2. Toxicities other than DLTs will be considered, including: AEs assessed as related to study drug treatment but not considered dose-limiting, the nature and frequency of toxicities, and the emergence of any specific category of toxicities.
3. Evidence of clinical activity, as available.
4. Available pharmacodynamic data.
5. Consideration will be given to select RP2D dose that will sustain E7046 exposure above IC50 or IC90 values for EP4 inhibition for the duration of dosing period.

If two or more potential RP2D dose levels cannot be distinguished using the criteria above, cohort expansion (see below) may take place at up to 2 dose levels to obtain data for up to 6 additional subjects per dose level. Selection of RP2D will be based on this larger dataset.

If serious related toxicities are observed in later cycles beyond Cycle 1 a reduction of the MTD and/or RP2D may be considered. This determination will be made by the investigators and the sponsor physician, taking into account all available data.

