#### 9.7.1.6 Dose Escalation Primary Endpoints Analyses

**Safety/tolerability profile** of E7046 will be assessed. The incidence of treatment-emergent adverse events (TEAEs) and SAEs together with all other safety parameters will be summarized, by dose levels.

**Maximum tolerated dose.** The incidence of DLTs by dose level will be tabulated. The MTD will be determined per protocol definition.

**RP2D.** The RP2D will be selected as described in [Section 9.1.1.4](#).

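### Crude TEAE percentages by dose level tend to make higher doses look less toxic when the RP2D is chosen, because the lower-dose cohorts have been followed longer

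*SAP*

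**What the plan says.** **TEAE measure.** SAP 5.6.3 plans an ever/never count: "The incidence of TEAEs will be reported as the number (percentage) of subjects with TEAEs within SOC and PT". A TEAE is "an AE that emerged during treatment (from first dose to 30 days after last dose of study drug", so the window differs from subject to subject. None of the tables listed there uses a window common to all subjects or a denominator in subject-time. Protocol 9.7.1.6 makes this a primary dose-escalation analysis: "The incidence of treatment-emergent adverse events (TEAEs) and SAEs together with all other safety parameters will be summarized, by dose levels".

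**Design.** Protocol 9.1.1.1: "E7046 will be tested in sequential escalating dose cohorts of 6 subjects per cohort". The first cohort is staggered: "If after 14 days of dosing no suspected severe immune reactions are observed, another 2 subjects" may start, and subjects 4 to 6 wait for the 21-day DLT evaluation of the first three. Later cohorts may dose at most one new subject per day, and DLT assessment must be agreed before each escalation (9.1.1.2). Treatment continues beyond Cycle 1 (9.1.3.3).

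**Decision.** Protocol 9.1.1.4: "Selection of the RP2D will take place after the last subject in the Dose Escalation part completes the Treatment Phase". That phase is the 21-day Cycle 1 (9.1.3.2). The second RP2D guideline takes in non-DLT toxicities, including how often they occur.

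**Exposure.** SAP 5.6.1: "Number of cycles completed, duration of treatment and cumulative total dose will be summarized by dose group". Nothing links this summary to the AE percentages.

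**Cutoff.** Protocol 9.7.1 sets the final cutoff at 6 cycles for the last enrolled subject, or early discontinuation. SAP 3.2 allows a cutoff once the last subject completes Cycle 1, or another date set by the sponsor and the primary investigator.

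**The concern.** An ever/never percentage grows with time observed. When the RP2D is chosen, the 125 mg cohort may have been followed for several cycles and the 750 mg cohort for barely more than one. Any toxicity that can start after Cycle 1 then has more chance to be counted at the lower doses, whatever the true effect of dose.

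This matters because the protocol itself expects that an MTD may not be reached (9.1 and 9.2), in which case the RP2D rests on integrated evaluation. Some toxicities are also kept out of the DLT count by definition: Grade 3 or higher diarrhea, nausea or vomiting of limited duration, and Grade 3 or lower irAEs that resolve within 7 days. Protocol 7.1.3.3 lists colitis with diarrhea as an anticipated effect. Such events bear on the choice of dose mainly through their frequency, and the error in that frequency favours the higher dose.

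**Working it through.** **Plan's own figure.** 4 cohorts × 6 = 24; 24 + 6 = 30; 24 + 16 = 40. This reproduces the stated sample size. The documents give no TEAE rate or follow-up ratio, so the risks and stopping rates below are assumptions.

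**1. Fastest calendar under 9.1.1.1.** Cohort 1 starts on days 0, 14, 14, 35, 35, 35. Each later cohort starts when the last subject of the one before completes 21 days, with one subject per day: 250 mg on days 56–61, 500 mg on days 82–87, 750 mg on days 108–113. The earliest RP2D selection is day 113 + 21 = 134.

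**2. Potential follow-up at day 134** (134 minus start day, averaged over the cohort):

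| Dose | Mean days | Cycles (days/21) | Ratio to 750 mg |
|---|---|---|---|
| 125 mg | 111.8 | 5.3 | 4.8 |
| 250 mg | 75.5 | 3.6 | 3.2 |
| 500 mg | 49.5 | 2.4 | 2.1 |
| 750 mg | 23.5 | 1.1 | 1.0 |

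Assumed slower accrual (one subject per 7 or 14 days in cohorts 2 to 4, with 7- or 14-day gaps between cohorts) raises the 125 to 750 mg ratio to between 5.8 and 6.2. Choosing the RP2D one cycle later lowers it: (111.8 + 21)/(23.5 + 21) = 3.0.

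**3. Equal risk at every dose, nobody stopping (upper bound).** Assume 10% risk per cycle. Expected incidence is the cohort mean of 1 − 0.9^(days/21). At 125 mg, 134, 120 and 99 days give 48.9%, 45.2% and 39.1%, so the mean is (48.9 + 2 × 45.2 + 3 × 39.1)/6 = 42.8%. Across the doses: 43/32/22/11%.

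**4. Equal risk, 25% stopping at the end of each cycle.** Count completed cycles on drug only. The chance of reaching the next cycle event-free and still on drug is q = 0.9 × 0.75 = 0.675, and incidence after n cycles is 0.10 × (1 − q^n)/(1 − q).
- 125 mg, n = 6, 5, 5, 4, 4, 4: (27.9 + 2 × 26.5 + 3 × 24.4)/6 = 25.7%
- 250 mg, n = 3: 21.3%
- 500 mg, n = 2: 16.8%
- 750 mg, n = 1: 10.0%

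Rounded: 26/21/17/10%. Counting events to 30 days after last dose, as the SAP window does, with an assumed median of 42 days on drug gives 30/27/21/11%. Restricted to Cycle 1, the incidence is 10% at every dose.

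**5. A true gradient.** Assume 10% per 21 days at 125 mg, median 63 days on drug, and the SAP's 30-day tail.

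| Hazard per level | Crude at day 134 | Cycle 1 only |
|---|---|---|
| × 1.5 | 34/39/41/33% | 10/15/21/30% |
| × 2 | 34/48/61/61% | 10/19/34/57% |

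In the first row a threefold rise in Cycle 1 risk looks flat in the crude figures. In the second the crude figures still rise up to 500 mg, but much less steeply.

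**6. The final report.**
- Protocol 6-cycle cutoff, no expansion: potential follow-up is 217 against 129 days (1.7-fold). With a median of 42 to 63 days on drug, time on drug differs only 1.1- to 1.2-fold. At equal 10% risk and median 63 days, crude incidence is 40/39/37/35%.
- SAP 3.2 cutoff, one cycle after a 6-subject expansion: potential follow-up is 138 against 50 days (2.8-fold), and time on drug differs 1.6- to 1.9-fold.

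**The case against.** A reader might infer that toxicity frequency must fall with dose by construction. The documents do not support that. It needs a hazard that is roughly constant over time and does not rise with dose. Step 5 shows crude percentages that are flat or rising when the true hazard rises, and events confined to Cycle 1 are largely unaffected.

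A reader might also infer that the plan selects the RP2D from the SAP 5.6.3 tables. It does not say so. Protocol 9.7 places the statistical analyses after database lock, no interim analysis is planned, and SAP 5.6 makes no formal comparison between doses. The RP2D is a joint, integrated judgement. What stands is that frequency is a named guideline and neither document defines any other measure of it.

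There are real safeguards. DLTs use a Cycle 1 window, apart from later events added by discussion. The MTD rests on DLTs, and the RP2D may not exceed it. Exposure is summarised by dose, AEs are listed by subject, and laboratory values and vital signs are tabulated by visit. Extra subjects may be enrolled, and serious later toxicity may lead to a lower MTD or RP2D. These limit the harm but do not put TEAE frequency on a common footing.

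The size is modest for any single term. With 6 subjects per cohort, 26% against 10% is about 1.5 against 0.6 expected subjects, a difference of roughly one. Adjacent doses differ by less than half a subject. The 43/32/22/11% series assumes that nobody stops treatment, which is unrealistic in progressing advanced cancer. The bias does, however, run in the same direction for every toxicity that can start late.

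**Conclusion.** The point holds in a limited form. At RP2D selection, crude TEAE percentages by dose level are biased toward making higher doses look less toxic and can flatten or mask a dose-toxicity gradient. The follow-up imbalance comes from the protocol's own calendar: 4.8-fold for 125 against 750 mg, but only 2.1-fold for 500 against 750 mg. The effect on incidence rests on assumptions: about 26/21/17/10% with 10% risk and 25% stopping per cycle, and at most 43/32/22/11% at that risk if no one stops, against 10% throughout in Cycle 1.

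The DLT and MTD determination is largely outside the problem. In the final report the imbalance mostly goes away under the protocol's 6-cycle cutoff, and a good part of it remains under the earlier SAP cutoff. This is a worthwhile, inexpensive improvement to the safety summaries and does not call the escalation design into question.

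**What to change.** - **SAP 5.6.3 and protocol 9.7.1.6:** add, by dose level, all TEAEs, Grade ≥3 TEAEs and treatment-related TEAEs restricted to Cycle 1 (Days 1–21), the window planned for every subject. Supplement these with an exposure-adjusted incidence (subjects with the event per subject-cycle at risk) to cover later events.
- **Protocol 9.1.1.4:** state that comparison of toxicity frequency between dose levels is informed by these summaries. The reference belongs here because SAP 5.6.3 is not tied to the RP2D decision.
- **All-time n (%) tables:** keep them as descriptive.
- **Data cutoffs:** reconcile protocol 9.7.1 with SAP 3.2.

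The cost is a few extra tables from data already collected, plus wording changes in both documents. No dose or clinical rule changes. The Cycle 1 table ignores late events. The exposure-adjusted rate covers them but assumes a roughly constant hazard and is imprecise with 6 subjects per cohort, so it should support the Cycle 1 table and not replace it.
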